### 9.10.5 Secondary Endpoint 1 – Target Protective NAC (Day 120), Cohorts 1-2

To evaluate secondary objective #1 demonstrate target protective concentration (NAC) value  $> 0.02$  U/mL (BoNT/A) or  $> 0.03$  U/mL (BoNT/B) at Day 120 (Cohorts 1-2), secondary endpoint #1 will be used:

## Statistical Analysis Plan (SAP)

---

To evaluate target protective concentration (NAC) value  $> 0.02$  U/mL (BoNT/A) or  $> 0.03$  U/mL (BoNT/B) at Day 120

At Visit 11 (Day 120), the frequency and percentage of subjects with a NAC  $> 0.02$  U/mL against BoNT/A, a NAC  $> 0.03$  against BoNT/B, and those with either a NAC  $> 0.02$  U/mL against BoNT/A or a NAC  $> 0.03$  U/mL against BoNT/B will be presented. Percentages will be based on the total number of subjects at the respective time point with evaluable concentrations. Summaries will be presented for each lot separately within each of the two active drug cohorts.

The PD population will be used for the analysis of this secondary endpoint.

### 9.10.6 Secondary Endpoint 2 – PD and ADA Evaluation, Cohorts 1-2

To evaluate secondary objective #2, to evaluate pharmacodynamic (PD) and anti-drug antibody (ADA) at pre-dose through the end of study (Cohorts 1-2), secondary endpoint #2 will be used.

The following PD parameter estimates for samples analyzed using the Battelle Mouse Neutralization Assay (MNA) method will be reported:

- $AUC_{(0-t)}$ : Area under the concentration time-curve to the last concentration above the lower limit of quantitation (reported in day\*U/mL)
- $C_{max}$ : Maximum observed concentration (reported in U/mL)
- $T_{max}$ : Time of maximum observed concentration (reported in days)
- $t_{1/2}$ : Terminal elimination half-life (reported in days)

PD parameters will be summarized by lot and active cohort using descriptive statistics against each serotype (BoNT/A and BoNT/B) separately. Parameters will be calculated and presented separately for Dose 1 and Dose 2 where applicable.

Additionally, NAC values will be summarized descriptively for each serotype separately at Baseline/Dosing [Visit 2 (Day 1)] pre-dose, Visit 3 (24 Hours), Visit 5 (Day 8), Visit 6 (Day 15), Visit 7 (Day 45) pre-dose, Visit 8 (Day 49), Visit 10 (Day 90), and Visit 11 (Day 120). Concentration-time profiles will be displayed graphically on linear and semi-log scales by serotype and active treatment group. One set of plots will include error bars (presented as SD) and one set will not include error bars.

The summary statistics used for all PD parameters and concentrations will include number of subjects (n), mean, SD, median, Q1, Q3, minimum, maximum, coefficient of variation (CV, presented in percentage, CV%), geometric mean (GM), the 95% CI of the GM, the geometric coefficient of variation (GCV, presented in percentage, GCV%), and the 95% CI of the GCV%.

The GM, 95% CI of GM, GCV%, and 95% CI of GCV% will be calculated using the following SAS® procedure:

```
proc ttest data=indata dist=lognormal;
```

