5. INVESTIGATIONAL PLAN

5.1. Study Design

This is a Phase 2, multicenter, randomized, double-blinded, placebo-controlled study to evaluate the safety, tolerability, pharmacodynamics (PD), and immunogenicity of a single dose (100 mg) and a repeat dose (50 mg and 100 mg) of G03-52-01 administered by IM injection(s) in adult subjects ([Appendix C](#)).

Approximately 625 subjects will be enrolled in this study to receive active product or placebo on Day 1 or Day 1 and Day 45, and will be randomized to the following concurrent cohorts:

- Cohort 1 (N=150, 75 lot #1, 75 lot #2): 50-mg dose
- Cohort 2 (N=150, 75 lot#1, 75 lot#2): 100-mg dose
- Cohort 3 (N=75): Placebo
- Cohort 4 (N=250): 100 mg dose or Placebo

The study will include up to 14-day screening period and an approximately 1-hour stay for Cohorts 1-3 and 8 hours stay for Cohort 4 in the clinic after dosing is complete for PK assessment and to ensure that no hypersensitivities or safety signals occur. Follow-up visits will occur at 24 hours and 72 hours post dose, and on Days 8, 15, 45, 49, 60, 90, 120, 150, 180, and 240 for Cohorts 1-3. For Cohort 4, follow-up visits will occur 24 hours, 72 hours, and on Days 8, 15, 30, 45, 90, and 120.

Safety Analysis

Safety labs will be drawn at pre-dose, 24 hours post dose, and on Days 15, 45 (before repeat-dose or placebo), 60, 120, and 240 for Cohort 1-3. Subjects in Cohort 4 will have safety labs drawn at screening and on Day 15, 45, and 120.

PD Analysis

PD samples will be collected for all subjects. Analysis will be completed by the Battelle Mouse Neutralization Assay (MNA) for Serotypes A and B.

Samples for subjects in Cohorts 1-3 will be tested at pre-dose, 24 hours post dose, and on Days 8, 15, 45 (before repeat-dose or placebo), 49, 90, and 120. The first 25 subjects randomized for each DP lot of 50 mg and 100 mg doses and placebo will be tested at all 8 timepoints. The remaining samples from the subjects who received either dose or lot of G03-52-01 (including placebo) will only be tested using MNA at pre-dose and Days 45, 90, and 120.

All subjects in Cohort 4 will have samples collected at pre-dose, 2 hours, 4 hours, 8 hours, 24 hours and on Days 30, 45, and 90. Samples will be analyzed for the first 30 subjects in Cohort 4, who receive active drug and complete the sample collection at 24 hours. See [Figure 2](#) and [Figure 3](#).

PK Analysis

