5.4.2. Randomization Procedures

Randomized treatment assignments will be generated by centralized randomization system. The system will be used each day that a subject, who has been screened and qualified at the site, returns for a study visit. Subjects will be randomized 2:2:1 to the following concurrent cohorts:

- Cohort 1: 50-mg dose of G03-52-01 on Day 1 and repeat 50-mg dose on Day 45 (N=150)
- Cohort 2: 100-mg dose of G03-52-01 on Day 1 and repeat 100-mg dose on Day 45 (N=150)
- Cohort 3: Placebo on Day 1 and placebo on Day 45 (N=75)

Within Cohorts 1 and 2, subjects will be randomized 1:1 to receive their study drug from Lots 1 or 2 of the drug. Within each of the 4 study drug dose/lots and the placebo cohort, subjects will be randomized 2:1 to provide PD or PK specimens at visits specified in the Schedule of Assessments ([Appendix A](#)).

Subjects in Cohort 4 will be randomized in a 4:1 to receive a single 100-mg dose of G03-52-01 or Placebo on Day 1 (N=250).

All individuals with access to study subjects or subject data will remain blinded until all data are entered and verified, and database is locked.

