Vital sign assessments will be performed at all in-clinic study visits, including systolic and diastolic blood pressure (BP), heart rate (HR), and oral temperature. During screening and follow-up, a measurement that is a Grade 1 (as referenced in Protocol G03-52-01-002, v4.0, 14Apr2024, Appendix B) may be repeated once if the principal investigator believes a transient condition led to the aberrant value. Vital signs obtained at screening will serve as baseline values for the subject. Grade 1 values are allowable unless deemed clinically significant by the study Investigator.

- **Electrocardiogram (ECG)**

A 12-lead ECG will be performed at screening and reviewed by the study PI or a co-Investigator to assess the cardiac status of a subject for eligibility for enrollment.

- **Laboratory Evaluations**

Laboratory assessment schedule will follow the Schedule of Assessments in Appendix A. Detailed laboratory tests can be found in Section 8.5.2 of Protocol G03-52-01-002, v4.0, 14Apr2024.

- **Pharmacodynamic (PD) and Pharmacokinetic (PK) Assays**

Blood samples for PD assessment will be collected at pre-dose, 24 hours post-dose, and on Days 8, 15, 45 (prior to dosing) 49, 90, and 120 for all subjects in Cohorts 1-3. The first 25 subjects randomized for each DP lot of 50 mg and 100 mg doses and placebo will be tested at all 8 timepoints. The remaining samples from the subjects who received either dose or lot of G03-52-01 (including placebo) will only be tested using MNA at pre-dose and Days 45, 90, and 120.

Blood samples for PD assessment will be collected at pre-dose, 2 hours, 4 hours, 8 hours, 24 hours, and on Days 30, 45, and 90 for all subjects in Cohort 4. Cohort 4 samples for the first 30 subjects, who receive active drug product and complete sample collection at 24 hours, will be tested at pre-dose, 2 hours, 4 hours, 8 hours, 24 hours, and on Days 30, 45, and 90. PD samples will be analyzed for neutralizing antibody concentration (NAC) using the validated Battelle MNA.

Blood samples for PK assessment will be collected at pre-dose, 24 hours and 72 hours post-dose, and on Days 8, 15, 45 (prior to dosing), 49, 90, and 120 for all subjects in Cohorts 1-3. The first 25 subjects randomized for each DP lot of 50 mg and 100 mg doses and placebo will be tested at all timepoints.

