## Statistical Analysis Plan (SAP)

---

```
var x;  
ods select ConfLimits;  
run;
```

, where `indata` is the data set with PD parameters and `x` is a parameter.

Additionally, PD parameters and NAC values will be listed separately at the subject level.

The PD population will be used for all pharmacodynamic tables, listings, and figures.

Immunogenicity (ADA) samples will be tested at Baseline/Dosing [Visit 2 (Day 1)] pre-dose, Visit 3 (24 Hours) and Visit 4 (72 Hours) post-dose, and at Visit 5 (Day 8), Visit 6 (Day 15), Visit 7 (Day 45) pre-dose, Visit 8 (Day 49), Visit 10 (Day 90), Visit 11 (Day 120), Visit 12 (Day 150), Visit 13 (Day 180), and Visit 14 (Day 240).

The frequency and percentage of subjects with a positive immunogenicity response will be summarized by time point across the active treatment arms. Additionally, anti-drug antibody titers will be summarized using continuous descriptive statistics [number of subjects (n), mean, SD, median, Q1, Q3, minimum, maximum, CV%, GM, GCV%, and the 95% CI of the GCV] by time point. Both the categorical and continuous ADA table summaries will include a subgroup analysis for only those subjects that have a negative immunogenicity response at baseline. Anti-drug antibody status and titer values will be listed by subject and time point.

The ITT population will be used for all immunogenicity summaries.

### 9.10.7 Secondary Endpoint 3 – Target Protective NAC (2 Hours), Cohort 4

To evaluate secondary objective #3, demonstrate target protective concentration (NAC) value of BoNT/A and BoNT/B at 4 and 8 hours post-dose (Cohort 4), secondary endpoint #3 will be used.

To evaluate the proportion of subjects with target protective concentration (NAC) value > 0.02 U/mL (botulinum neurotoxin [BoNT]/A) or > 0.03 U/mL (BoNT/B) at 2 hours post dose

At the 4 Hour and 8 Hour post-dose time points, the frequency and percentage of subjects with a NAC > 0.02 U/mL against BoNT/A, a NAC > 0.03 against BoNT/B, and those with either a NAC > 0.02 U/mL against BoNT/A or a NAC > 0.03 U/mL against BoNT/B will be presented. Percentages will be based on the total number of subjects at the respective time point with evaluable concentrations.

The PD population will be used for the analysis of this secondary endpoint.

### 9.10.8 Secondary Endpoint 4 – PK Evaluation, Cohort 4

To evaluate secondary objective #4, to assess pharmacokinetics (PK) at pre-dose through end of study (Cohort 4), secondary endpoint #4 will be used.

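### The eight-visit NAC profile in SAP 9.10.6 changes who is measured at four of its seven steps, so its decline and Dose 2 step are not purely within-subject change

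*SAP*

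**What the plan says.** **Testing.** Protocol 5.1 says: "The first 25 subjects randomized for each DP lot of 50 mg and 100 mg doses and placebo will be tested at all 8 timepoints". SAP 3.4 repeats this and says that remaining subjects' samples "will only be tested using MNA at pre-dose and Days 45, 90, and 120". Each active dose/lot group has 75 planned subjects (SAP Table 1).

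**Analysis.** SAP 9.10.6 says that "NAC values will be summarized descriptively for each serotype separately at Baseline/Dosing" and then lists the other seven visits: 24 hours and Days 8, 15, 45, 49, 90 and 120. For the figures it says "Concentration-time profiles will be displayed graphically on linear and semi-log scales by serotype and active treatment group". One set of plots carries SD error bars, so the curves are group summaries. The analysis set is fixed by "The PD population will be used for all pharmacodynamic tables, listings, and figures". SAP 7.1.4 defines that population by sufficient evaluable samples, with no minimum number of visits and no reference to the first 25. SAP 10 lists no relevant change from the protocol.

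**A conflict on the denominator.** Protocol 5.1 says "PD samples will be collected for all subjects", but Protocol 5.4.2 says that, within each dose/lot group and placebo, "subjects will be randomized 2:1 to provide PD or PK specimens". The first gives 75 PD subjects per group at the fully tested visits, the second about 50.

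**The concern.** A mean curve over time is naturally read as what happens to a group of people. Here the group changes along the curve. Three of the changes fall where the curve is most informative: the decline after Dose 1 (Day 15 to 45), the step across Dose 2 (Day 45 to 49) and the decline after Dose 2 (Day 49 to 90). Any difference between the first 25 and the later subjects, whether by chance or by enrolment period, site or body weight, appears on the plot as a faster or slower decline or a larger or smaller Dose 2 step. What is at stake is how a descriptive secondary display is read.

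**Working it through.** **1. Counts.** The listed visits number eight, matching the plan's own figure, and five groups of 75 give the 375 subjects stated for Cohorts 1-3. Planned n per active dose/lot group:

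| | Pre-dose | 24 h | D8 | D15 | D45 | D49 | D90 | D120 |
|---|---|---|---|---|---|---|---|---|
| PD from all subjects | 75 | 25 | 25 | 25 | 75 | 25 | 75 | 75 |
| 2:1 PD/PK split (75 × 2/3 = 50) | 50 | 25 | 25 | 25 | 50 | 25 | 50 | 50 |

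The second row assumes that the first 25 lie within the 50 PD subjects. On either reading the set changes at four of the seven steps: pre-dose to 24 h, Day 15 to 45, Day 45 to 49, and Day 49 to 90. At a 75-subject visit, 50/75 = 67% of the weight comes from subjects absent at the neighbouring 25-subject visits (50% on the 2:1 reading).

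**2. Chance shift.** The documents give no NAC variability, so the log-scale SD s is an assumption. The SE of the first-25 log mean minus the all-N log mean is s × √(1/25 − 1/N).

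- N = 75: the factor is 0.163. For s = 0.4, SE = 0.065 and the 95% limits on the ratio of geometric means, exp(±1.96 × SE), are +14%/−12%. For s = 0.6, SE = 0.098 and the limits are +21%/−17%.
- N = 50: the factor is 0.141. The limits are about +12%/−11% (s = 0.4) and +18%/−15% (s = 0.6).

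On a constant set of 25 this component is zero.

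**3. If later enrolees differ (assumption).** The geometric mean at a 75-subject visit moves by the factor (1 − d)^(2/3) when the later 50 run a fraction d lower. For d = 10%, 20% and 30% the shifts are −7%, −14% and −21%. The documents do not suggest such a drift.

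**4. BLQ rule (SAP 8.3).** BLQ values count as zero before the first measurable value and as missing afterwards, and zeros become 0.001 in geometric means. A first-25 subject who is BLQ at Day 45 after an earlier measurable value is therefore dropped. A sparsely tested subject has only the pre-dose sample before Day 45, so with no measurable value there, the same Day 45 result enters as zero. Let q be the assumed BLQ fraction at Day 45 in both sets and g the geometric mean of quantifiable values. Then:

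- sparse log mean = (1 − q) ln g + q ln 0.001
- pooled log mean = [25(1 − q) ln g + 50 × sparse log mean] / [25(1 − q) + 50]

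At q = 2% and g = 0.05 U/mL, the pooled Day 45 geometric mean is 0.0474, 5% below the first 25. At q = 10% and g = 0.5 U/mL it is 0.326, 35% below. On arithmetic means, where zeros stay zero, the ratio is 75(1 − q)/(75 − 25q): 73.5/74.5 = 0.987 at q = 2% and 67.5/72.5 = 0.931 at q = 10%, so 1% to 7% lower.

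**5. Precision of a visit-to-visit change.** With within-subject correlation ρ, the SE of a Day 45/Day 15 log ratio is s√(1/25 + 1/75 − 2ρ/75) for the mixed sets and s√((2 − 2ρ)/25) for the matched 25. The mixed SE is 1.00, 1.20, 1.41 and 1.91 times the matched SE at ρ = 0.5, 0.7, 0.8 and 0.9. Below 0.5 the mixed set is the more precise: the ratio is 0.90 at ρ = 0.3.

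**The case against.** The strongest reply is that this is an all-available-data summary in a trial with no formal testing (SAP 6). The first 25 are set by randomisation order, not outcome, so without drift or BLQ values each visit mean is unbiased. The tables report n at each visit, and every NAC value is listed by subject. All of that stands, and it limits the weight of the point.

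Three stronger readings are tempting, but the documents do not support them.

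- *That the artefact imitates lot-to-lot variability.* Lots are randomised concurrently, 1:1:1:1:1 (SAP 3.3), under the same first-25 rule. At each visit early subjects are compared with early subjects, or all with all. Drift is shared in expectation, and what remains is sampling error.
- *That a half-life or Dose 2 ratio will be biased.* No section plans either from group means. SAP 9.10.6 plans separate PD parameters, including half-life, for each dose.
- *That the artefact cannot be told from pharmacology.* The n in the tables and the subject listings would let a reader recover a matched view.

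Three other defences are incomplete. The interim report (Protocol 11.2, SAP 4.1) covers 125 = 5 × 25 subjects, probably close to the fully tested set. SAP 4.1 defines them by completion through Day 120, though, and an interim display does not correct the final one. Reading SAP 7.1.4 as excluding four-visit subjects would give a constant 25, but it would also cut the Day 45 and Day 90 primary endpoint, which uses the same population (SAP 9.10.3). The SAP says no such thing. Table and figure templates are in a separate document (SAP 1) and may contain a restriction, but the SAP text does not require one.

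**Conclusion.** The point holds as a cheap improvement to a descriptive secondary display. The eight-visit NAC table and profile for Cohorts 1-2 join different sets of subjects at four steps, on either reading of the PD denominator. Chance alone can separate the two sets' geometric means by roughly 10-20% at the 95% limits if the log SD is 0.4-0.6. Unequal BLQ handling could lower the pooled Day 45 geometric mean by a further 5-35% if 2-10% of values are BLQ and the quantifiable geometric mean is 0.05-0.5 U/mL. It has no effect if no Day 45 value is BLQ. All these inputs are assumptions.

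The protective-NAC rates at Days 45, 90 and 120 are each computed within one visit, so joining the visits does not affect them. How BLQ values enter their denominators is a separate question, not settled here.

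**What to change.** In SAP 9.10.6, base the eight-visit NAC profile plots and their table on the subjects assigned full eight-visit MNA testing (the first 25 per dose/lot), and show n at each visit. Report pre-dose and Days 45, 90 and 120 for all assayed subjects in a separate table, not joined to those points. Leave the protective-NAC rates on all assayed subjects. While editing, state whether the all-assayed number per group is 75 or about 50, since Protocol 5.1 and 5.4.2 disagree.

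This does not change the BLQ rule, but it removes the difference in handling between fully and sparsely tested subjects from the curve. The cost is SAP wording, one flag variable and one extra table, with no new samples or assays. The downside is that the Day 45, 90 and 120 points in the profile rest on 25 subjects, although the all-assayed values are still reported alongside.

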## Statistical Analysis Plan (SAP)

---

```
var x;  
ods select ConfLimits;  
run;
```

, where `indata` is the data set with PD parameters and `x` is a parameter.

Additionally, PD parameters and NAC values will be listed separately at the subject level.

The PD population will be used for all pharmacodynamic tables, listings, and figures.

Immunogenicity (ADA) samples will be tested at Baseline/Dosing [Visit 2 (Day 1)] pre-dose, Visit 3 (24 Hours) and Visit 4 (72 Hours) post-dose, and at Visit 5 (Day 8), Visit 6 (Day 15), Visit 7 (Day 45) pre-dose, Visit 8 (Day 49), Visit 10 (Day 90), Visit 11 (Day 120), Visit 12 (Day 150), Visit 13 (Day 180), and Visit 14 (Day 240).

The frequency and percentage of subjects with a positive immunogenicity response will be summarized by time point across the active treatment arms. Additionally, anti-drug antibody titers will be summarized using continuous descriptive statistics [number of subjects (n), mean, SD, median, Q1, Q3, minimum, maximum, CV%, GM, GCV%, and the 95% CI of the GCV] by time point. Both the categorical and continuous ADA table summaries will include a subgroup analysis for only those subjects that have a negative immunogenicity response at baseline. Anti-drug antibody status and titer values will be listed by subject and time point.

The ITT population will be used for all immunogenicity summaries.

### 9.10.7 Secondary Endpoint 3 – Target Protective NAC (2 Hours), Cohort 4

To evaluate secondary objective #3, demonstrate target protective concentration (NAC) value of BoNT/A and BoNT/B at 4 and 8 hours post-dose (Cohort 4), secondary endpoint #3 will be used.

To evaluate the proportion of subjects with target protective concentration (NAC) value > 0.02 U/mL (botulinum neurotoxin [BoNT]/A) or > 0.03 U/mL (BoNT/B) at 2 hours post dose

At the 4 Hour and 8 Hour post-dose time points, the frequency and percentage of subjects with a NAC > 0.02 U/mL against BoNT/A, a NAC > 0.03 against BoNT/B, and those with either a NAC > 0.02 U/mL against BoNT/A or a NAC > 0.03 U/mL against BoNT/B will be presented. Percentages will be based on the total number of subjects at the respective time point with evaluable concentrations.

The PD population will be used for the analysis of this secondary endpoint.

### 9.10.8 Secondary Endpoint 4 – PK Evaluation, Cohort 4

To evaluate secondary objective #4, to assess pharmacokinetics (PK) at pre-dose through end of study (Cohort 4), secondary endpoint #4 will be used.

PK summaries will include the NX01, NX02, NX11, XB10, XB18, and XB23 mAbs. The following PK parameter estimates for sample tested by ECLA or ELISA will be reported at each of the aforementioned time points:

- $AUC_{(0-t)}$ : Area under the concentration time-curve to the last concentration above the lower limit of quantitation (reported in day\*ng/mL)
- $AUC_{(0-\infty)}$ : Area under the concentration time-curve extrapolated to infinity (reported in day\*ng/mL)
- $C_{max}$ : Maximum observed concentration (reported in ng/mL)
- Kel: Elimination rate constant (reported in 1/day)
- $t_{1/2}$ : Terminal elimination half-life (reported in days)
- CL/F: Total clearance (reported in L/day)
- $V_d/F$ : Volume of distribution (reported in L)

Concentrations of each mAb will be summarized descriptively in tables by active treatment group and time point. Concentration-time profiles will be displayed graphically on linear and semi-log scales by mAb and active treatment group. One set of plots will include error bars (presented as SD) and one set will not include error bars.

The summary statistics used for all PK parameters and concentrations will include number of subjects (n), mean, SD, median, Q1, Q3, minimum, maximum, CV%, GM, 95% CI of the GM, GCV%, and the 95% CI of the GCV. PK parameters will be presented by Dose 1 and Dose 2 where applicable.

Additionally, PK parameters and concentrations will be listed separately at the subject level.

The PK population will be used for all pharmacokinetic tables, listings, and figures.

### 9.10.9 Secondary Endpoint 5 – PD and ADA Evaluation, Cohort 4

To evaluate secondary objective #5, to evaluate pharmacodynamics (PD) and anti-drug antibody (ADA) at pre-dose through the end of study (Cohort 4), secondary endpoint #5 will be used:

Descriptive statistics of determined PD and ADA timepoints

The following PD parameter estimates for samples analyzed using the Battelle Mouse Neutralization Assay (MNA) method will be reported:

- $AUC_{(0-t)}$ : Area under the concentration time-curve to the last concentration above the lower limit of quantitation (reported in day\*U/mL)
- $C_{max}$ : Maximum observed concentration (reported in U/mL)
- $T_{max}$ : Time of maximum observed concentration (reported in days)
- $t_{1/2}$ : Terminal elimination half-life (reported in days)

Dose 1 PD parameters will be summarized for the Cohort 4 active treatment group using descriptive statistics against each serotype (BoNT/A and BoNT/B) separately.

